8.1. Adverse Events and Unanticipated Problems

The study team will be responsible for identifying and reporting all serious adverse events, protocol deviations/violations, and unanticipated problems to the IRB, DSMB, and funding agency promptly, as appropriate. In order for the PI to remain blinded, expert critical care clinicians (attending physician, fellow physician, or advanced practice provider) trained by PI [name] will lead adverse event monitoring and reporting, with the support of the project manager. We will proactively perform surveillance of three adverse events – life-threatening acidemia, and death or cardiac arrest within 24 hours of trial enrollment. Adverse events possibly or likely related to the intervention will be reported immediately to the Data and Safety Monitoring Board (DSMB, see below) within 7 days of occurrence, if fatal or life-threatening. Unanticipated problems will be reported to DSMB within 14 days of identification.

8.2. Data and Safety Monitoring Board

An important safeguard to protect research participants is the development of a plan for ongoing data and safety monitoring to anticipate, and protect against, any human subjects research concerns that

may arise. We will convene a DSMB comprising noted experts in critical care, palliative care, and biostatistics to guard against the possibility of any unforeseen risks arising during the study. Members of the DSMB will not be involved in the conduct of the trial. Once convened, the DSMB will perform several duties. First, they will review and approve the research protocol and plans for data and safety monitoring prior to the study's implementation. Second, they will evaluate the progress of the trial. This will include assessment of data quality, participant accrual and retention, participant risk versus benefit, and study outcomes. Third, they will make recommendations to ensure that any identified issues are appropriately addressed. The DSMB will meet after 9 months and 18 months (one-third and two-thirds of the way through the trial enrollment. We will charge DSMB members with using their judgment in simultaneously considering many data points in making decisions about trial design modifications and trial continuation or termination. The PI ([name]), the project manager, and the data analyst ([name]), will participate in all DSMB meetings as non-voting members. The PI, assisted by the project manager, will be responsible for maintaining communication between the DSMB, the IRB, and study sites.

Our DSMB members to monitor the scientific conduct of the study are as follows:

- **[name], MSc** Associate Professor of Medicine in the Division of Allergy, Pulmonary and Critical Care Medicine at Vanderbilt University (DSMB Chair)
- **[name]** Assistant Professor of Preventive Medicine and Director of Clinical Research Informatics at the Keck School of Medicine University of Southern California
- **[name]** Professor of Medicine in the Division of Pulmonary and Critical Care Medicine, Department of Medicine at Johns Hopkins University and Director of the Johns Hopkins Adherence Research Center (JHARC) and the Director of the Cystic Fibrosis Adherence Program
- **[name], MS, PhD** Professor of Biostatistics within the University of California San Francisco Division of Oral Epidemiology & Dental Public Health and Division of Epidemiology and Biostatistics

8.3. Interim Analyses

The trial will be monitored routinely for issues of data quality and study conduct (including participant enrollment and technical issues with EHR order sets) via monthly data extraction and analysis by our research team's data manager, [name]. We will conduct two interim analyses – after approximately 9 months and 18 months (one-third and two-thirds of the trial duration, respectively) – of two study outcomes: (1) fidelity to LPV (primary outcome, as specified above), and (2) in-hospital mortality.

We do not plan to stop the trial early for evidence of effectiveness of the implementation strategies because doing so would reduce our power for secondary analyses and analyses of effect modification. We will propose to stop the trial for early evidence of harm based on in-hospital mortality.

8.4. Institutional Review Board (IRB)

The convened University of Pennsylvania IRB (FWA: 00004028) have approved the INPUT study (#833340) with a waiver of informed consent and waiver of patient notification. Penn IRB will provide regulatory oversight for the trial activities at the study hospitals. All modifications to the protocol will be submitted to both IRBs for approval prior to implementation.

## I. Background and rationale

Of the million Americans who undergo invasive mechanical ventilation (MV) annually within intensive care units (ICUs), 30-35% die in the hospital, and survivors commonly have long-term cognitive, emotional and physical impairments. Although potentially life-saving, MV can also injure the lungs. Strategies of “lung-protective ventilation” (LPV) aim to minimize harm by delivering low tidal volumes (the amount of air per breath delivered by the ventilator) and limiting the artificial pressures in the lungs. LPV was first proven effective in patients with acute respiratory distress syndrome (ARDS), a severe form of respiratory failure associated with pneumonia, sepsis, and other common illnesses. A multicenter randomized trial published in 2000 demonstrated an absolute mortality reduction of 10%, shortened duration of MV, and reduced organ failure rates. These findings have since been replicated and incorporated into international guidelines. However, fifteen years later, more than one-third of ARDS patients overall, and up to 81% in some ICUs, do not receive LPV.

Multiple studies across diverse ICUs have consistently identified two key barriers to LPV utilization: limited knowledge about LPV, and tendencies to prescribe LPV only when ARDS is definitively diagnosed, in part due to theoretical concerns about potential harms of LPV. However, definitive diagnosis of ARDS is challenging. And recent evidence suggests that (1) concern for harm among patients without ARDS is likely unwarranted, and (2) LPV may in fact reduce lung injury and mortality even among patients without ARDS.

## II. Objectives

The trial's overall objective is to compare simple, low-cost, scalable strategies grounded in behavioral economic theory to (a) increase utilization of evidence-based LPV for MV patients, (b) gauge the process-oriented and clinical benefits of targeted vs. non-targeted approaches to changing behavior, (c) explore how clinician and environmental contextual factors affect LPV utilization, and (d) determine how patient factors such as type and severity of disease affect both LPV utilization and its associated outcomes.

Overall, we hypothesize that strategies that encourage clinicians to use LPV among all MV patients will mitigate the aforementioned barriers of knowledge gaps and diagnostic uncertainty, thereby increasing LPV utilization across diverse settings among patients with and without ARDS.

## III. Design and randomization

- Stepped-wedge, cluster-randomized, pragmatic clinical trial of three EHR-based implementation strategies designed to increase utilization of LPV among MV patients. (see **Appendix A**).
  - 12 ICUs across five UPHS hospitals, which all currently have access to an EHR-based algorithm that identifies patients with ARDS and prompt physicians to employ LPV via a clinical dashboard and through ICU telemedicine support, will sequentially add two of three EHR-based implementation strategies to further promote LPV utilization among all MV patients.
  - Study ICUs will be randomly assigned to first receive one of two physician-directed strategies: either a **default order set (Strategy A)** or **physician-targeted accountable justification strategy (Strategy B)**. ICUs will be assigned to one of six wedges, thereby determining the date on which they adopt their assigned EHR-based strategy (**Figure 3**). The first wedge will begin in the fourth month of the trial phase. Six months after adoption, all ICUs will add on an **RT-targeted accountable justification strategy (Strategy C)**. The trial monitoring period will last 27 months. This design enables comparisons of outcomes before and after implementation *within* ICUs, as well as at a given point in time *among* ICUs which will have been randomly assigned to different strategies.
  - All ICUs will contribute a minimum of 3 months of baseline data prior to intervention and utilize two strategies in combination for a minimum of 3 months.

- After the 27-month trial monitoring period, all study ICUs will contribute 6 months of post-intervention data for analysis of sustainment, during which time the research team will have no further contact with the study ICUs. Therefore, the study intervention period will be 27 months, and the entire study duration will be 33 months.
- 12 ICUs across five UPHS hospitals will be randomized into six 2-ICU clusters by computerized random-number generation using R random number generator function.
- To form clusters with balanced patient volume and primary outcome baseline value, ICUs will be matched in pairs based on: 1) ICU patient volume (ICUs will be categorized as large or small based on whether their annual patient volume is above or below the median) and 2) the baseline value of the primary outcome (ICUs will be categorized as high or low rates of adherence to LPV based on whether their median rate is above or below the median). The six ICU clusters will then be randomly assigned to receive either Strategy A or B and then randomly assigned to represent wedges 1 through 6, with each wedge transitioning to the intervention phase in sequential fashion.
- We selected the timing of each wedge transition such that each wedge (2-ICU cluster) contributes a minimum of 12 weeks of data under the control condition prior to intervention implementation.

## IV. Population

The trial will have two subject populations.

- The first group includes mechanically ventilated patients admitted to study ICUs during the pragmatic trial of interventions that will be applied at the level of the ICU.
- The second population includes mechanically ventilated patients admitted to study ICUs in the 6 months after intervention phase has been completed. During this observational phase, there will be no additional experimental interventions or contact with the study team.

## V. Primary outcome and analytic method

### a. Primary outcome

The primary outcome variables will be (1) **fidelity** to LPV, measured by the percentage of time in the first 72 hours of mechanical ventilation that a patient is exposed to tidal volume  $\leq 6.5$  cc/kg ideal body weight and (2) **sustainability** of the effects of the implementation strategies, measured as the percentage of time in the first 72 hours of MV that a patient is exposed to tidal volume  $\leq 6.5$  cc/kg ideal body weight among MV patients each month during 6 months after the study monitoring period ends.

We will consider episodes separated by less than or equal to 2 hours as a single episode. We will count the period of time that a patient is extubated as if the patient is on minimal settings, and will therefore subtract that period of time from the denominator of the primary outcome variable (if it falls in the first 72 hours).

### b. Primary hypotheses

Hypothesis 1: The default order panel will increase utilization of LTVV compared to usual care.

Hypothesis 2: The accountable justification order panel will increase utilization of LTVV compared to usual care.

### c. Primary analytic sample

For the purpose of the trial, the **primary analytic sample** will be limited to episodes of MV among patients who meet the following criteria:

1. Aged 18 and over; **AND**
2. Admission to 1 of the 12 participating ICUs; **AND**
3. Undergoing mechanical ventilation

Any episodes of MV that meet the eligibility criteria above will be **excluded** from the primary analysis if they meet any of the following criteria:

1. The episode of MV lasts less than 12 hours, because we believe that the evidence-based practice may not apply to these patients nor alter their outcomes.
2. The patient is on minimal settings for the entirety of MV, defined as a spontaneous mode (e.g., pressure support ventilation) with pressure support  $\leq 10$  cmH2O, **AND** PEEP  $\leq 8$  cmH2O, **AND** FiO2  $\leq 50\%$ , because the clinical significance of spontaneous tidal volumes is unknown and low tidal volumes may not be beneficial or desirable.
3. Goals of care are documented as comfort measures only (as identified by presence of an order for “Comfort Care” in the EHR) during the first 72 hours during episode of MV, because mechanical ventilation is managed differently during care focused exclusively on comfort and low tidal volume ventilation may not be appropriate, nor would it likely influence clinical outcomes.
4. There is no height documented in the EHR at the time of initiation of MV, because we will be unable to estimate ideal body weight, a necessary parameter to calculate the primary outcome, and because they will not receive the interventions.
5. The height documented is less than 4 feet, because the formula for ideal body weight does not hold true below this height.

#### **d. Primary analysis**

The primary analytic approach will use a **modified intention-to-treat (mITT)** approach. We choose this approach because we have observed in preliminary studies in the study ICUs that some patients will start MV and receive MV orders prior to ICU admission, and because of the constraints of the EHR to deploy the strategies, such episodes will not be eligible to be exposed to the intervention. Because ICUs differ in their percentages of patients who will and will not be eligible for exposure to the strategies, and these patient groups may be systematically different, in the primary analysis, we will limit the population to patients who receive a new MV order within 72 hours of enrollment (the time of the start of MV in the ICU).

The unit of analysis for primary study outcome (and all implementation outcomes) will be the episode of mechanical ventilation.

- Patients may have multiple episodes of MV if the patient is ventilated multiple times. We will include only the first eligible episode during a hospital admission for the primary analysis. We will calculate the proportion of patients who receive multiple episodes or multiple admissions. We expect the proportion will be very small, based on prior data from study ICUs.

The primary comparisons of interest will be:

- strategy A vs. strategy B
- strategy A vs. control
- strategy B vs control
- strategy A vs. strategy A combined with strategy C
- strategy B vs. strategy B combined with strategy C

Secondary comparisons of interest are control versus A + C, control versus B + C, and control versus C alone among patients who are not exposed to the order panel strategies (i.e., in the ITT but not mITT population).

We will use a linear mixed-effects model for primary analysis. The structure of the model is as follows:

$$Y_{ijk} = \mu + \alpha_i + \beta_j + X_{ij}\theta + e_{ijk}$$

where  $Y_{ijk}$  denotes the percentage from individual  $k$  at time  $j$  from cluster  $i$ ;  $\alpha_i$  is a random effect for cluster  $i$ ;  $X_{ij}$  is the treatment indicator for cluster  $i$  at time  $j$ ,  $\theta$  is the treatment effect and the residual is  $iid$  with  $e_{ijk} \sim N(0, \sigma_e^2)$ . Since the intervention occurs over time, the proportion of clusters exposed to the intervention gradually increases. We will include step as a fixed effect ( $\beta_j$ ) in the model to adjust for the potential confounding factor from calendar time.

In addition, to account for the matched pair randomization, which was done to balance patient volume and estimated baseline adherence to low tidal volume ventilation per cluster, we will include variables for the total number of observations within a cluster per step and estimated baseline adherence rates per cluster.

All analyses will be conducted with adjustment for pre-specified cluster-level and patient-level covariates that exist prior to the patient meeting eligibility criteria (**Table 1; see Appendix B for additional details**). We will include the adjustment terms  $\varphi_1 Z_{ijk}$  and  $\varphi_2 W_{ij}$ , where  $Z$  and  $W$  represent vectors of patient and cluster characteristics that could be predictors of outcomes, to adjust for any imbalance from clusters' and patients' characteristics. Note that the index  $j$  in these matrices allows us to include time-varying covariates. To account for the possibility of a delay in an intervention exerting its effects, we will change  $X_{ij}\theta$  to  $X_{ijl}\theta_l$  to account for the number of months since the intervention was introduced in cluster  $i$ . We intend to include these additional terms (with pre-specified patient and ICU characteristics) in our primary models to augment precision in estimating the treatment effects.

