**Table 1. Factors for adjustment**

|  |
|--|
| Age  |
| Sex  |
| COVID-19 status (categorical)  |
| LAPS2 severity of illness measured at the time of hospital admission |
| LAPS2 severity of illness measured at the time of enrollment         |
| ICU admission source   |
| Hospitalization duration prior to ICU admission                      |
| Code status (categorical)  |
| Location of start of MV episode                                      |
| Height   |

If the fitted model violates the 'normality of residuals' assumption, we will use a suitable inference approach such as permutation test or bootstrap confidence intervals. In addition, we will explore alternative modeling approaches to account for non-normality if needed, e.g. two part mixed effects models.

All analyses will be conducted using R (Vienna, Austria).

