### a. Analysis of secondary outcomes

Secondary implementation outcomes will be analyzed at the level of the episode and will be modeled as per the primary analysis, using generalized linear mixed effects models, with appropriate links for binary and categorical dependent variables.

For example, for a binary outcome, the model has the form

$$\text{logit}(Y_{ijk}) = \mu + \alpha_i + \beta_j + X_{ij}\theta$$

Model parameters are similar to those in the primary outcome analysis.

Effectiveness outcomes and potential adverse effects will be analyzed at the level of the episode of MV. Binary and categorical effectiveness outcomes (mortality and discharge disposition) will be modeled per the primary analysis.

For MV duration, ICU length of stay, and hospital length of stay, because of a high mortality rate (~30%), we will model these outcomes as a composite with death using a “free days” approach. In other words, for duration of MV, for example, we will use ventilator-free days within 30 days, which will be calculated as the number of days a patient is alive and not on invasive mechanical ventilation for 30 days from the start of enrollment. We will use similar calculations for ICU-free days (alive and not admitted to the study ICU) and hospital-free days (alive and not admitted to the study hospital). For patients who are discharged alive and off the ventilator prior to 30 days, we will assume they are alive and off the ventilator for the remainder of 30 days. For patient who are discharged on the ventilator prior to 30 days, we will assume they remain on the ventilator for the remainder of 30 days. For patients who are discharged to hospice (home or facility), we will assume they have died upon the day of discharge.

We will explore the population where patients have multiple episodes of MV, as patients with multiple admissions may have higher risk of mortality. We will also examine the patient outliers in terms of MV

duration, ICU length of stay and hospital length of stay. Depending on the proportion, we may include multiple episodes into the study by creating a variable about the number of episodes.

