### **b. Timing of analysis and adjustment of significance level**

Two interim analyses will be conducted after approximately 9 months and 18 months after trial launch (one-third and two-thirds of the trial duration, respectively) of two study outcomes: (1) fidelity to LPV (primary outcome, as specified above), and (2) in-hospital mortality. All interim analyses will be performed at the level of an episode of mechanical ventilation. For the open portion of the DSMB meeting, we will summarize data for the entire study population in aggregate, including patient characteristics, key patient outcomes, and the primary study outcome (percentage of time during the first 72h of MV in the ICU that the patient has tidal volume less than or equal to 6.5cc/kg IBW). We will also report adverse event rates among in aggregate.

To evaluate mortality by group, we will first report unadjusted mortality rates by group, and then proceed in a stepwise fashion with up to three risk-adjusted models:

- Model 1: We will use a generalized linear mixed effects model to estimate unadjusted mortality accounting for design issues; that is, including a random effect for ICU, a fixed effect for study group assignment, and a fixed effect for step (to account for potential confounding from calendar time).
- Model 2: We will use a generalized linear mixed effects model to preliminarily test whether study group assignment is associated with mortality after risk adjustment. As in the above model, we will include a random effect for ICU, a fixed effect for study group assignment, and a fixed effect for step (to account for potential confounding from calendar time). Given variability in case mix, we will also include the following covariates for risk adjustment: age, sex, race, source of admission to the hospital, Elixsauser score and LAPS2 score on the day of study enrollment.

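### Interim and final mortality models use different, non-nested covariate lists without explanation, and the comorbidity score is named only at the interim

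*SAP*

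**What the plan says.** SAP V.d sets the general rule: "All analyses will be conducted with adjustment for pre-specified cluster-level and patient-level covariates". It points to "Table 1; see Appendix B for additional details". Outside Table 1, the same section adds design terms ("we will include variables for the total number of observations within a cluster per step and estimated baseline adherence rates per cluster") and allows a vector of cluster characteristics.

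The patient-level list, "Table 1. Factors for adjustment", has ten entries: age, sex, COVID-19 status, two LAPS2 scores ("LAPS2 severity of illness measured at the time of hospital admission" and "LAPS2 severity of illness measured at the time of enrollment"), ICU admission source, hospital time before the ICU, code status, where ventilation started, and height. The list in protocol 7.2.1 is shorter and likewise names no comorbidity score.

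For the final analysis, SAP X.a says: "Binary and categorical effectiveness outcomes (mortality and discharge disposition) will be modeled per the primary analysis".

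For the interim analyses, SAP XIV.b gives Model 2 a random ICU effect, fixed effects for group and step, and, because case mix varies, these covariates: "age, sex, race, source of admission to the hospital, Elixsauser score and LAPS2 score on the day of study enrollment". I read the fifth item as the Elixhauser comorbidity score. Model 3, where the error-spending boundaries are introduced, follows only if Model 2 shows excess mortality of at least 5% at p<0.2. Its covariates are not stated.

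**The concern.** The SAP judged that case mix varies enough to adjust interim mortality for comorbidity. That reason applies equally to the final comparison, yet the score is absent from the final list and nothing explains why. The two LAPS2 terms do not obviously replace it, because protocol 7.2.1 describes LAPS2 as a laboratory-based acute physiology score, not a measure of chronic disease.

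The design gives this some weight. Within every ICU, control time comes before strategy time. The step effect removes the calendar trend common to all ICUs, but not a change in case mix confined to some of them. Protocol 7.2.1 itself foresees local change: a new hospital tower affecting two study ICUs, and COVID-19 disruptions. The fixed effects planned for those events mark periods and places. They do not measure how ill patients were beforehand.

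At stake are the final contrasts for mortality and discharge disposition, and for the ventilator-, ICU- and hospital-free days that incorporate death. Interpretation is also affected. If the mortality estimate moves between an interim look and the final analysis, a reader cannot tell whether the data or the covariate list moved it. With a logit link, conditional odds ratios from different covariate sets are not on quite the same scale, even without confounding.

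**Working it through.** **1. The plan's linked figures.** SAP XIV.b gives 0.0007 and 0.0161 (one-sided) for the interim looks and 0.0451 for the final analysis. The Lan-DeMets O'Brien-Fleming-type spending function is α(t) = 2[1 − Φ(z₁₋α/₂/√t)]. With α = 0.05 and t = 1/3, 2/3 and 1, cumulative spending is 0.00069, 0.01637 and 0.05000. Solving for the boundaries by multivariate normal integration gives z = 3.200, 2.141 and 1.695, with nominal one-sided p = 0.0007, 0.0161 and 0.0451. All three stated levels reproduce, so they form one three-look sequence at one-sided 0.05. No covariate list enters this calculation.

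**2. The two mortality lists compared.**
- In both (3): age, sex, LAPS2 at enrollment.
- Interim Model 2 only (3): race, source of hospital admission, Elixhauser score.
- Table 1 only (7): COVID-19 status, LAPS2 at hospital admission, ICU admission source, hospital time before the ICU, code status, location of ventilation start, height.

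Totals are 3 + 3 = 6 interim covariates and 3 + 7 = 10 Table 1 covariates. Neither list contains the other.

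**3. Illustrative size of unadjusted drift.** Control mortality of 25% is from SAP XII.b. The other inputs are assumptions, because the documents give none:
- odds ratio for death per SD of comorbidity, beyond what Table 1 already explains: 1.2 to 1.6;
- drift in mean comorbidity between control and strategy months in one strategy's ICUs, relative to the others: 0.1 to 0.3 SD.

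Spurious log odds ratio = ln(OR per SD) × drift. Control odds = 0.25/0.75 = 0.3333.
- Low end: ln(1.2) × 0.1 = 0.0182, odds ratio 1.02. Odds 0.3333 × 1.0184 = 0.3395, risk 25.34%, a shift of +0.34 points.
- High end: ln(1.6) × 0.3 = 0.1410, odds ratio 1.15. Odds 0.3333 × 1.1514 = 0.3838, risk 27.74%, a shift of +2.74 points.

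These values require the whole drift to be shared by a strategy's ICUs. Suppose instead that 0.1 to 0.3 SD is the spread of independent drifts, and that a strategy has six ICUs (an equal split, which the documents do not state). Dividing the log odds ratios by √6 = 2.449 gives 0.0074 and 0.0576, or about 0.14 and 1.1 points, as a typical size in either direction. For scale, the Model 2 trigger is 5 points.

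**The case against.** The strongest reply is that the final model may be the better adjusted of the two. Table 1 is longer, and code status, COVID-19 status, a second LAPS2 and hospital time before the ICU are plausible predictors of death that Model 2 lacks. This stands. A reader might infer from the missing score that final risk adjustment is weaker overall, but the documents report no measure of fit or discrimination by which to rank non-nested lists. Nor is Table 1 the whole model, given the cluster-level and design terms. Appendix B is not in the text available to me, so I assume nothing about its contents. It should be checked for a comorbidity term.

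A reader might also infer that changing covariates invalidates the sequential significance levels. The documents do not support that. Model 2 is a preliminary screen, the boundaries attach to Model 3, and Model 3's covariates are unstated. No type I error consequence can be derived.

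Third, strategy and wedge are randomized, so ICU-specific drift is mainly chance imbalance, not systematic bias. This also stands, and it is why the 2.7-point figure should not be read as an expected bias. With 12 ICUs, though, chance imbalance need not be small.

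Finally, SAP IX plans a random cluster-by-time term and an analysis with ICU as a fixed effect. The first addresses time effects that differ across ICUs and the second stable ICU differences. Neither adjusts for patients' comorbidity.

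**Conclusion.** The concern holds in a limited form. For one outcome, monitored and then finally analyzed within one plan, the SAP names two covariate lists that share three items, and gives no reason. The comorbidity score appears only at the interim; code status and COVID-19 status are among the items that appear only in the final analysis. As written, the final mortality contrasts leave comorbidity drift in particular ICUs unadjusted.

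The size is unknown from the documents. The range of 0.3 to 2.7 points rests on the assumed odds ratios and on drift shared by a strategy's ICUs. Independent drift gives roughly 0.1 to 1.1 points with six ICUs per strategy. Every value is below the 5-point trigger. Mortality is a secondary outcome, and no sample size or power figure changes. The case for acting is protection against chance imbalance, some gain in efficiency, and a final estimate that can be compared with the interim ones. The conclusion assumes that Appendix B adds no comorbidity measure.

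**What to change.** Add the Elixhauser score to the Table 1 covariates for final hospital mortality, discharge disposition, and ventilator-, ICU- and hospital-free days. Restrict it to conditions present at hospital admission, in line with the SAP V.d requirement that covariates predate eligibility. State this as the single mortality covariate list and use it at any interim look still to be held, in Model 2 and, explicitly, in Model 3. The first look has already taken place (SAP XII.a) and cannot be changed. If the sponsor prefers to keep two lists, the SAP should give the reason and add a sensitivity analysis of final mortality with the score included.

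The cost is mainly SAP wording, since the interim plan already calls for the score. The documents do not say how the score is derived, so the data manager must confirm that conditions present at admission can be separated from later ones. The one downside is that, without that restriction, complications arising after enrollment could be adjusted away.
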